## **2. TRIAL OBJECTIVES AND ENDPOINTS**

### **2.1 MAIN OBJECTIVES, PRIMARY AND SECONDARY ENDPOINTS**

#### **2.1.1 Main objectives**

The main objective of this trial is to investigate the absolute bioavailability of 100 mg of BI 765080 administered in healthy male subjects as subcutaneous (SC) injection versus intravenous (IV) infusion.

[figure not shown]
#### **2.1.2 Primary endpoints**

The following pharmacokinetic parameters will be determined for BI 765080:

[figure not shown]
- $AUC_{0-tz}$  (area under the concentration-time curve of the analyte in plasma over the time interval from 0 to the last quantifiable data point)
- $C_{max}$  (maximum measured concentration of the analyte in plasma)

#### **2.1.3 Secondary endpoints**

- $AUC_{0-\infty}$  (area under the concentration-time curve of the analyte in plasma over the time interval from 0 extrapolated to infinity)
- To assess safety and tolerability of BI 765080: Occurrence of drug-related adverse event

Proprietary confidential information © 2021 Boehringer Ingelheim International GmbH or one or more of its affiliated companies

[figure not shown]

#### **2.2.2.2 Safety and tolerability**

Safety and tolerability of BI 765080 will be assessed based on:

- Adverse events (including clinically relevant findings from the physical examination)
- Safety laboratory tests
- 12-lead ECG
- Vital signs (blood pressure, pulse rate)

Proprietary confidential information © 2021 Boehringer Ingelheim International GmbH or one or more of its affiliated companies

### **3. DESCRIPTION OF DESIGN AND TRIAL POPULATION**

#### **3.1 OVERALL TRIAL DESIGN AND PLAN**

The study will be performed as a randomised, open-label, matched parallel group trial in healthy male subjects in order to compare subcutaneous injection administration (T) to intravenous infusion (R). The treatments will be one single 100 mg BI 765080. For details, refer to Section [4.1](#).

An overview of all relevant trial activities is provided in the [Flow Chart](#). For visit schedule and details of trial procedures at selected visits, refer to Sections [6.1](#) and [6.2](#), respectively.

#### **3.2 DISCUSSION OF TRIAL DESIGN, INCLUDING THE CHOICE OF CONTROL GROUP**

This study will explore the absolute bioavailability, safety, tolerability and pharmacodynamics following intravenous (IV) infusion or subcutaneous (SC) injection of BI 765080 in matched pairs of healthy male subjects (matching is done based on age and body weight, see Section [3.3](#)). By dosing test and reference treatment to a matched pair on the same day the influence of confounding factors can be reduced to a minimum.

The trial will be conducted open-label. Blinding is not possible because the treatments are distinguishable. The open-label treatment is not expected to bias results, since the study endpoints are derived from measurement of plasma concentrations of the analyte, which are provided by a bioanalytical laboratory that is blinded to treatment allocation.

#### **3.3 SELECTION OF TRIAL POPULATION**

It is planned that 28 healthy male subjects (14 subjects with IV and 14 subjects with SC) will enter the study to have at least 12 evaluable subjects available in each group. They will be recruited from the volunteers' pool of the trial site.

Participants in SC and IV groups will be matched for age (18-36 or 37-55 years at screening) and body weight ( $\pm 10\%$  inclusive). That means, that the 2 subjects of one matched pair are either 18-36 years (inclusive) or 37-55 years old (inclusive) and that the difference of their body weight does not exceed 10% (e.g. 80 kg and 88 kg).

Only Caucasian male subjects will be included in the study.

A log of all subjects enrolled into the trial (i.e. who have signed informed consent) will be maintained in the ISF irrespective of whether they have been treated with investigational drug or not.

##### **3.3.1 Main diagnosis for trial entry**

The trial will be performed in healthy subjects.

##### **3.3.2 Inclusion criteria**

Subjects will only be included in the trial if they meet the following criteria:

Proprietary confidential information © 2021 Boehringer Ingelheim International GmbH or one or more of its affiliated companies

1. Healthy Caucasian male subjects according to the assessment of the investigator, as based on a complete medical history, a physical examination, vital signs (BP, PR), 12-lead ECG, and clinical laboratory tests
2. Age of 18 to 55 years (inclusive)
3. BMI of 18.5 to 29.9 kg/m^2 (inclusive)
4. Signed and dated written informed consent prior to admission to the study, in accordance with GCP and local legislation

### **3.3.3 Exclusion criteria**

Subjects will not be allowed to participate, if any of the following general criteria apply:

1. Any finding in the medical examination (including ECG) deviating from normal and assessed as clinically relevant by the investigator
2. Repeated measurement of systolic blood pressure outside the range of 90 to 140 mmHg, diastolic blood pressure outside the range of 50 to 90 mmHg, or pulse rate outside the range of 45 to 90 bpm
3. Any laboratory value outside the reference range that the investigator considers to be of clinical relevance
4. Any evidence of a concomitant disease assessed as clinically relevant by the investigator
5. Gastrointestinal, hepatic, renal, respiratory, cardiovascular, metabolic, immunological or hormonal disorders
6. Diseases of the central nervous system (including but not limited to any kind of seizures or stroke), and other relevant neurological or psychiatric disorders
7. History of relevant orthostatic hypotension, fainting spells, or blackouts
8. Chronic or relevant acute infections
9. History of relevant allergy or hypersensitivity (including allergy to the trial medication or its excipients)
10. Use of drugs with a long half-life (more than 24 h) within 30 days or less than 10 half-lives of the respective drugs prior to administration of trial medication
11. Use of drugs within 10 days of planned administration of trial medication that might reasonably influence the results of the trial (including drugs that cause QT/QTc interval prolongation)
12. Intake of an investigational drug in another clinical trial within 60 days of planned administration of investigational drug in the current trial, or concurrent participation in another clinical trial in which investigational drug is administered
13. Smoker (more than 10 cigarettes or 3 cigars or 3 pipes per day)
14. Inability to refrain from smoking on specified trial days
15. Alcohol abuse (consumption of more than 30 g per day)
16. Drug abuse or positive drug screening

Proprietary confidential information © 2021 Boehringer Ingelheim International GmbH or one or more of its affiliated companies

17. Blood donation of more than 100 mL within 30 days of planned administration of trial medication or intended blood donation during the trial
18. Intention to perform excessive physical activities within one week prior to the administration of trial medication or during the trial
19. Inability to comply with the dietary regimen of the trial site
20. A marked baseline prolongation of QT/QTc interval (such as QTc intervals that are repeatedly greater than 450 ms in males) or any other relevant ECG finding at screening
21. A history of additional risk factors for *Torsade de Pointes* (such as heart failure, hypokalaemia, or family history of Long QT Syndrome)
22. Subject is assessed as unsuitable for inclusion by the investigator, for instance, because the subject is not considered able to understand and comply with study requirements, or has a condition that would not allow safe participation in the study
23. Male subjects with WOCBP partner who are unwilling to use a highly effective method of birth control from time point of administration of trial medication until 90 days thereafter. Highly effective methods of birth control are:
  - Male subject is sexually abstinent
  - Male subjects is vasectomised (vasectomy at least 1 year prior to enrolment), plus condom in male subject
  - Use of intrauterine device (IUD) or intrauterine hormone-releasing system (IUS) by female partner
  - Use of progestogen-only hormonal contraception by female partner that inhibits ovulation (only injectables or implants), plus condom in male subject
  - Use of combined (estrogen and progestogen containing) hormonal contraception by female partner that prevents ovulation (oral, intravaginal or transdermal), plus condom in male subject
  - Female partner is surgically sterilised (including hysterectomy)
  - Female partner is postmenopausal, defined as no menses for 1 year without an alternative medical cause)

Subjects are required to use condoms to prevent unintended exposure of the partner (both, male and female) to the study drug via seminal fluid. Male subjects should use a condom throughout the study and for 90 days after investigational medicinal product (IMP) administration.

Alternatively, true abstinence is acceptable when it is in line with the subject's preferred and usual lifestyle.

If a subject is usually not sexually active but becomes active, with their partner, they must comply with the contraceptive requirements detailed above.

Male subjects should not donate sperm for the duration of the study until at least 90 days after IMP administration.

In addition, the following SARS-CoV-2-specific exclusion criteria apply:

24. A positive PCR test for SARS-CoV-2 or clinical symptoms suggestive for this disease prior to the admission.

For study restrictions, refer to Section [4.2.2](#).

### **3.3.4 Withdrawal of subjects from treatment or assessments**

Subjects may discontinue trial treatment or withdraw consent to trial participation as a whole ('withdrawal of consent') with very different implications; please see Sections [3.3.4.1](#) and [3.3.4.2](#) below.

If a subject is removed from or withdraws from the trial prior to the administration of trial medication, the data of this subject will not be entered in the case report form (CRF) and will not be reported in the clinical trial report (CTR). If a subject is removed from or withdraws from the trial after the administration of trial medication, this will be documented and the reason for discontinuation must be recorded in the CRF; in addition, the data will be included in the CRF and will be reported in the CTR.

At the time of discontinuation, a complete end of trial examination will be performed, if possible, and the information will be recorded in the CRF. If the discontinuation occurs before the end of the REP (see Section [1.2.4](#)), the discontinued subject should if possible be questioned for AEs and concomitant therapies at or after the end of the REP in order to ensure collection of AEs and concomitant therapies throughout the REP, if not contrary to any consent withdrawal of the subject.

#### **3.3.4.1 Discontinuation of trial treatment**

An individual subject will discontinue trial treatment if:

1. The subject wants to discontinue trial treatment, without the need to justify the decision
2. The subject has repeatedly shown to be non-compliant with important trial procedures and, in the opinion of both, the investigator and sponsor representative, is not willing or able to adhere to the trial requirements in the future.
3. The subject needs to take concomitant medication that interferes with the investigational medicinal product or other trial treatment
4. The subject can no longer receive trial treatment for medical reasons (such as surgery, adverse events [AEs], or diseases)
5. The subject has an elevation of AST and/or ALT  $\geq$ 3-fold ULN and an elevation of total bilirubin  $\geq$ 2-fold ULN (measured in the same blood sample) and/or needs to be followed up according to the DILI checklist provided in the ISF
6. An AE or clinically significant laboratory change or abnormality occurs that the investigator assesses as warranting discontinuation of treatment. This may include cases of sustained symptomatic hypotension (BP  $<90/50$  mmHg) or hypertension (BP  $>180/100$  mmHg), clinically relevant changes in ECG requiring intervention, or unexplained hepatic enzyme elevations at any time during the trial

Proprietary confidential information © 2021 Boehringer Ingelheim International GmbH or one or more of its affiliated companies

In addition to these criteria, the investigator may discontinue subjects at any time based on his or her clinical judgment.

If new efficacy or safety information becomes available, Boehringer Ingelheim will review the benefit-risk-assessment and, if needed, pause or discontinue the trial treatment for all subjects or take any other appropriate action to guarantee the safety of the trial subjects.

#### **3.3.4.2 Withdrawal of consent to trial participation**

Subjects may withdraw their consent to trial participation at any time without the need to justify the decision. If a subject wants to withdraw consent, the investigator should be involved in the discussion with the subject and explain the difference between trial treatment discontinuation and withdrawal of consent to trial participation, as well as explain the options for continued follow up after trial treatment discontinuation, please see Section [3.3.4.1](#) above

#### **3.3.4.3 Discontinuation of the trial by the sponsor**

Boehringer Ingelheim reserves the right to discontinue the trial at any time for any of the following reasons (if reasons 4 and/or 5 are met, the trial should be discontinued immediately):

1. Failure to meet expected enrolment goals overall or at a particular trial site
2. The sponsor decides to discontinue the further development of the investigational product
3. Deviation from GCP, or the CTP, or the contract with BI impairing the appropriate conduct of the trial.
4. New toxicological findings, serious adverse events, or any safety information invalidating the earlier positive benefit-risk-assessment.
5. More specifically, the trial will be terminated if more than 50% of the subjects have drug-related and clinically relevant adverse events of moderate or severe intensity, or if at least 1 drug-related serious adverse event is reported
6. Further dosing will be stopped if at least 2 subjects at one group (14 subjects) have relevant individual QT prolongations, i.e. a QTc increase of greater than 60 ms from baseline in connection with absolute QT or QTc greater than 500 ms, as confirmed by a repeat ECG recording
7. Occurrence of severe non-serious adverse events considered as drug-related by the investigator in 2 subjects of one group (14 subjects)

The investigator / trial site will be reimbursed for reasonable expenses incurred in case of trial termination (except if item 3 applies).

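### Stopping criterion 5 states no denominator; counted over all subjects, it cannot fire for moderate events confined to one route in complete pairs

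*Protocol*

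**What the plan says.** Protocol Section 3.3.4.3 lists the reasons for which the sponsor may discontinue the trial. Four of them matter here.

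- **Item 4** covers "any safety information invalidating the earlier positive benefit-risk-assessment" and has no number attached.
- **Item 5** has two limbs. The first is the percentage rule: "the trial will be terminated if more than 50% of the subjects have drug-related and clinically relevant adverse events of moderate or severe intensity". The second is "or if at least 1 drug-related serious adverse event is reported".
- **Item 6** stops further dosing for confirmed QT prolongation in "at least 2 subjects at one group (14 subjects").
- **Item 7** concerns severe, non-serious, drug-related events "in 2 subjects of one group (14 subjects").

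The list opens with the instruction that "if reasons 4 and/or 5 are met, the trial should be discontinued immediately". Items 4 and 5 are therefore binding once met.

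The plan is to enter "28 healthy male subjects (14 subjects with IV and 14 subjects with SC") (Section 3.3). Subjects are randomised 1:1 within matched pairs (Section 7.6), and both members of a pair are dosed on the same day (Section 3.2). Each subject receives one dose (Section 4.1.4).

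No section of the protocol or SAP defines the denominator of item 5. Section 1.4 relies on preset stopping criteria but points to Section 3.1, which holds none. Section 3.3.4.3 is presumably meant.

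**The concern.** Items 6 and 7 name the group and its size. Item 5 refers only to the subjects. Counting everyone in the trial is the natural reading, but it is not stated, and the two readings give opposite answers in the case a route comparison should anticipate: tolerability trouble with one route and not the other.

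SC is the route to plan for. The first-in-human trial was intravenous only (Section 1.3) and reported no drug-related adverse events (Section 1.2.3). The protocol reports no human SC data, and local tolerability after SC injection is one of its stated reasons for the trial.

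Item 7 covers severe events only, item 6 covers QT only, and the second limb of item 5 covers drug-related serious events only. A cluster of moderate, non-serious, non-QT events in the SC group has no numeric rule other than the percentage limb of item 5. If that limb cannot reach its threshold, stopping depends on judgement. At stake is the protection of healthy volunteers not yet dosed.

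**Working it through.** **Inputs from the protocol.** 14 SC and 14 IV subjects (Section 3.3); 1:1 within pairs (Section 7.6); same-day dosing of a pair (Section 3.2); a strict threshold of more than 50% (Section 3.3.4.3). The documents give no SC event rate, so every SC rate below is an assumption.

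**Step 1: counts needed.**
- All subjects: 14/28 = 50.0% does not exceed 50%; 15/28 = 53.6% does.
- One group: 7/14 = 50.0% does not; 8/14 = 57.1% does.

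**Step 2: events confined to SC, all-subjects reading.** After n complete pairs the largest possible share is n/(2n) = 50% for every n from 1 to 14. The limb cannot fire on a running count of complete pairs or on the final 28. Incomplete pairs are an exception: 14/27 = 51.9% with one IV subject missing, or 15/29 = 51.7% with one extra SC replacement. Each then requires every SC subject to be affected.

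**Step 3: chance of a numeric stop for SC-only events.** Let p be the SC rate of moderate or severe drug-related events and s the severe part of it, with no serious events, no QT events and none in IV.
- Per-group limb: P(Bin(14, p) ≥ 8).
- Item 7: P(Bin(14, s) ≥ 2) = 0.153 at s = 5% and 0.415 at s = 10%.
- Either one: P(severe ≥ 2) + P(X ≥ 8 and severe ≤ 1), where X ~ Bin(14, p) and severe given X ~ Bin(X, s/p).

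| Severe rate s | Reading of item 5 | p = 30% | 50% | 70% | 90% |
|---|---|---|---|---|---|
| 0 | all subjects | 0 | 0 | 0 | 0 |
| 0 | per group | 3% | 40% | 91% | >99.9% |
| 5% | all subjects (item 7 only) | 15% | 15% | 15% | 15% |
| 5% | per group | 17% | 46% | 91% | >99.9% |
| 10% | all subjects (item 7 only) | 42% | 42% | 42% | 42% |
| 10% | per group | 42% | 59% | 93% | >99.9% |

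The gap is widest when the events are moderate. Item 7 closes part of it as severe events become more common.

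**Step 4: allowing some IV events.** Zero drug-related events in 36 treated subjects (Section 1.2.3) gives a one-sided 95% upper bound of 1 − 0.05^(1/36) = 8.0%. With IV rates of 2% to 8% and no severe events, P(X_SC + X_IV ≥ 15) is below 0.01% at p = 30%, 0.01% to 0.2% at 50%, 0.3% to 3% at 70%, and 7% to 30% at 90%.

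**Step 5: who could benefit.** Eight SC subjects must already have been dosed, so at most 14 − 8 = 6 pairs (12 subjects) remain. If each outcome were known before the next pair was dosed, the mean number of undosed pairs at the eighth case, given that it occurs, is 1.7, 3.0 and 5.1 at p = 50%, 70% and 90%. The protocol gives no interval between pairs, so the true number could be zero.

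**Step 6: cost of a per-group trigger.** If both groups share a rate p, the chance that at least one group reaches 8 of 14 is 1 − (1 − P(Bin(14, p) ≥ 8))². The comparison is P(Bin(28, p) ≥ 15).

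| Common rate p | At least 8 of 14 in either group | At least 15 of 28 |
|---|---|---|
| 10% | 0.003% | <0.001% |
| 20% | 0.5% | 0.008% |
| 30% | 6.2% | 0.8% |

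**The case against.** The best reply is that item 5 is clear and deliberate. Items 6 and 7 specify a group and item 5 does not; item 5 terminates the whole trial, so a count over the whole trial is coherent. A less sensitive trial-level rule is the sponsor's to choose. Item 5 also opens as a specification of item 4, which carries the same instruction to stop immediately. The trial is open-label, so an SC cluster would be seen. Section 3.3.4.1 adds that, on new safety information, the sponsor "will review the benefit-risk-assessment and, if needed, pause or discontinue the trial treatment for all subjects". Finally, nothing in the documents suggests that 8 or more of 14 SC subjects would have moderate drug-related events.

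Much of this stands. The intended denominator is unknown, the high SC rates are assumptions, and the sponsor could stop for an SC-only signal. A reader might infer that the trial has no means of stopping for toxicity in one route; the documents do not support that, given items 4, 6 and 7, the serious-event limb of item 5 and the benefit-risk review. What remains is narrower. A stop that is mandatory once met cannot act, on its ordinary reading, in the one-route case, and the remaining cover for moderate events rests on judgement.

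A reader might also infer that replacing the limb with a fixed 8 of 14 would lose nothing. That holds only against a fixed denominator of 28, where 15 cases must put at least 8 in one group (7 + 7 = 14). Item 5 does not fix the denominator. On a running count with events in both routes, 5 of 8 dosed is 62.5% and would fire after four pairs, whereas a fixed 8 of 14 would not.

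**Conclusion.** The concern holds as a minor gap in the mandatory percentage rule. Item 5 leaves its denominator unstated. Read over all subjects, it cannot fire in complete pairs for moderate, non-serious, non-QT drug-related events confined to one route, even at 14 of 14. Under the assumed SC rates of 50% to 90% with no severe or IV events, that is a 0% chance of a numeric stop against 40% to over 99.9% with a per-group trigger. The difference narrows if severe events are common, or if IV events also occur at high SC rates.

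The practical benefit is bounded by the 6 pairs that could remain undosed. The documents do not show that the sponsor intended a per-group count, so this is an ambiguity with a consequence and not a demonstrated wrong number. The PK estimates and their confidence intervals are not affected.

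**What to change.** Amend the first limb of item 5 so that its denominator reads: *more than 50% of all subjects dosed, or at least 8 of the 14 subjects of one group*. Leave the event definition and the serious-event limb as they are.

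Keeping the existing limb beside the new one means that no current trigger is lost, including an early one on a running count. Counting over subjects dosed makes the first limb a running count; if the sponsor means a fixed 28, the text should say so.

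The cost is one phrase in a protocol amendment and a higher chance of stopping. Against a fixed 15 of 28, with the same rate in both groups, the chance rises from under 0.001% to 0.003% at 10%, from 0.008% to 0.5% at 20%, and from 0.8% to 6.2% at 30%. The new limb is a fixed count, so its chance does not depend on how often it is checked. The same amendment could correct the cross-reference in Section 1.4, a separate clerical point.

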#### **3.3.5 Replacement of subjects**

In case more than two subjects per treatment group do not complete the trial, the Clinical trial leader together with the Trial Pharmacokineticist and the Trial Statistician are to decide, if and how many subjects will be replaced. A replacement subject will be assigned a unique

[figure not shown]
Proprietary confidential information © 2021 Boehringer Ingelheim International GmbH or one or more of its affiliated companies

trial subject number and will be assigned to the same treatment as the subject he replaces. Matching conditions (body weight, age) have to be considered for replacement subjects. Subjects may not be replaced if they drop out for safety reasons, e.g. increase in liver transaminases.

